### 13.3.2 Blood chemistry parameters

| Parameter                   | UCB Conventional Units  | SI Units  | CF     |
|-----------------------------|---|---|--------|
| AST (SGOT)                  | ≥ 3 times of ULN  | ≥ 3 times of ULN  | N/A    |
| ALT (SGPT)                  | ≥ 3 times of ULN  | ≥ 3 times of ULN  | N/A    |
| ALP                         | For < 17 y: ≥ 2 times of ULN, if normal range adjusted to the age range;
For ≥ 17 y: ≥ 3 times of ULN                              | For < 17 y: ≥ 2 times of ULN, if normal range adjusted to the age range;
For ≥ 17 y: ≥ 3 times of ULN                  | N/A    |
| GGT                         | ≥ 3 times of ULN, if baseline value ≤ 3 times of ULN  | ≥ 3 times of ULN, if baseline value ≤ 3 times of ULN  | N/A    |
| BUN                         | ≥ 30 mg/dL  | ≥ 10.71 mmol/L  | 0.357  |
| Urea                        | ≥ 60 mg/dL  | ≥ 10.02 mmol/L  | 0.167  |
| Creatinine                  | For < 17 y: ≥ 1.5 mg/dL;
For ≥ 17 y: ≥ 2.0 mg/dL   | For < 17 y: ≥ 132.6 umol/L;
For ≥ 17 y: ≥ 176.8 umol/L   | 88.4   |
| Creatinine clearance (calc) | For < 12 y: < 70 ml/min (Schwartz) (a)
For ≥ 12 y: < 70 ml/min (Cockcroft) (b)                               | For < 12 y: < 70 ml/min (Schwartz) (a)
For ≥ 12 y: < 70 ml/min (Cockcroft) (b)                   | N/A    |
| Total bilirubin             | ≥ 2.0 mg/dL   | ≥ 34.2 umol/L   | 17.1   |
| Glucose                     | ≤ 50 mg/dL or ≥ 180 mg/dL   | ≤ 2.775 mmol/L or ≥ 9.99 mmol/L   | 0.0555 |
| Total Protein               | For ≥ 1 m to < 6 m: ≤ 3.6 g/dL or ≥ 7.8 g/dL
For ≥ 6 m to < 17 y: ≤ 4.7 g/dL or ≥ 9.5 g/dL
For ≥ 17 y: ≤ 4.5 g/dL or ≥ 9.0 g/dL | For ≥ 1 m to < 6 m: ≤ 36 g/L or ≥ 78 g/L
For ≥ 6 m to < 17 y: ≤ 47 g/L or ≥ 95 g/L
For ≥ 17 y: ≤ 45 g/L or ≥ 90 g/L | 10     |
| Albumin                     | For < 17 y: ≤ 2.4 g/dL or ≥ 6.5 g/dL
For ≥ 17 y: ≤ 2.5 g/dL or ≥ 6.5 g/dL  | For < 17 y: ≤ 24 g/L or ≥ 65 g/L
For ≥ 17 y: ≤ 25 g/L or ≥ 65 g/L  | 10     |
| Globulin                    | For < 17 y: ≤ 1.2 g/dL or ≥ 5.0 g/dL
For ≥ 17 y: ≤ 1.5 g/dL or ≥ 5.0 g/dL  | For < 17 y: ≤ 12 g/L or ≥ 50 g/L
For ≥ 17 y: ≤ 15 g/L or ≥ 50 g/L  | 10     |
| Sodium                      | For < 17 y: ≤ 120 mEq/L or ≥ 155 mEq/L
For ≥ 17 y: ≤ 115 mEq/L or ≥ 155 mEq/L  | For < 17 y: ≤ 120 mmol/L or ≥ 155 mmol/L
For ≥ 17 y: ≤ 115 mmol/L or ≥ 155 mmol/L                                      | 1      |
| Potassium                   | For < 17 y: ≤ 3.0 mEq/L or ≥ 6.5 mEq/L
For ≥ 17 y: ≤ 3.0 mEq/L or ≥ 5.8 mEq/L  | For < 17 y: ≤ 3.0 mmol/L or ≥ 6.5 mmol/L
For ≥ 17 y: ≤ 3.0 mmol/L or ≥ 5.8 mmol/L                                      | 1      |
| Calcium                     | For < 17 y: ≤ 7 mg/dL or ≥ 11.5 mg/dL
For ≥ 17 y: ≤ 7 mg/dL or ≥ 15.5 mg/dL  | For < 17 y: ≤ 1.75 mmol/L or ≥ 2.875 mmol/L
For ≥ 17 y: ≤ 1.75 mmol/L or ≥ 3.875 mmol/L                                | 0.25   |

|   |   |   |        |
|---|---|---|--------|
| Uric Acid   | For < 12 y:        ≥ 8 mg/dL
For ≥ 12 y:        ≥ 8 mg/dL (F); ≥ 9.5 mg/dL (M) | For < 12 y:        ≥ 475.84 umol/L
For ≥ 12 y:        ≥ 475.84 umol/L (F); ≥ 565.06 umol/L (M) | 59.48  |
| Cholesterol   | ≥ 300 mg/dL   | ≥ 7.77 mmol/L   | 0.0259 |
| HDL   | ≤ 25 mg/dL  | ≤ 0.65 mmol/L   | 0.0259 |
| LDL   | ≥ 200 mg/dL   | ≥ 5.18 mmol/L   | 0.0259 |
| Triglycerides   | ≥ 300 mg/dL   | ≥ 3.42 mmol/L   | 0.0114 |
| 
(a) Schwartz equation (patients <12):    Cr Cl ml/min = [Height (cm) * 0.55] / serum creatinine
 
(b) Cockroft equation (patients ≥12):    Male: Cr Cl ml/min = [(140-age) x body weight (kg)] / (72 x serum creatinine),
Female: Cr Cl ml/min = [(140-age) x body weight (kg)] / (72 x serum creatinine) x 0.85
 
ALT=alanine aminotransferase; ALP=Alkaline phosphatase; AST=aspartate aminotransferase; BUN=blood urea nitrogen; CR CL=creatinine clearance;
GGT=Gamma-glutamyl transpeptidase; HDL=High-density lipoprotein; LDL=low-density lipoprotein; SGOT=serum glutamic oxaloacetic transaminase;
SGPT=serum glutamic pyruvic transaminase; ULN=Upper Limit of Normal
 |   |   |        |

This document cannot be used to support any marketing authorization application and any extensions or variations thereof.

### 13.3.3 Urinalysis

Qualitative urine parameters are generally reported by a descriptive score, which differs among laboratories. For data analysis purpose, a four-point scale is used. Five-point, six-point, or seven-point scales will be collapsed into a four-point scale first. A value is considered possibly clinically significant treatment emergent abnormal if an upward shift of at least 2 degrees from the baseline occurs under investigational treatment. To collapse the results in a five-point scale into a four-point scale, the lowest two positive results will be combined (see example below). For results reported with a scale of more than five-point, please consult your study physician for how to collapse into four-point scale.

| Original Five-point Scale | Four-point Scale         |
|---------------------------|--------------------------|
| Negative/None             | Negative/None            |
| Trace/Rare/Mild/A Few     | Trace/1+/Rare/Mild/A Few |
| 1+                        |                          |
| 2+/Mod                    | 2+/Mod                   |
| 3+/Sev                    | 3+/Sev                   |

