### 11.3.2 Macroscopic urinalysis

Quantitative urinalysis parameters will be summarized in the same manner as hematology and blood chemistry parameters. Response categories are negative, 1+, 2+, and 3+ for the qualitative urinalysis parameters occult blood, leukocytes, glucose, protein, and ketones and negative and positive for nitrates. Outcome values for these parameters are mapped to the levels Negative, 1+, 2+, and 3+ as follows for purposes of summary tables and the determination of PCST:

| Category | Definition   |
|----------|--|
| Negative | “Negative”, “NEGATIVE”, or other outcomes that clearly reflect a negative finding  |
| 1+       | “1+”, “+”, “Trace”, “TRACE”, or other outcomes that clearly reflect trace amount   |
| 2+       | “2+” or “++”   |
| 3+       | “3+”, “+++”, or other outcomes that clearly reflect the data above 3+ (eg, “4+”, “5+” etc) or more than 4 plus signs (eg, “++++”, “+++++” etc) |

For qualitative urinalysis parameters (occult blood, leukocytes, glucose, protein, ketones, and nitrates), the number and percentage of subjects with each response category will be summarized for Baseline, Study Entry, each scheduled visit during the Evaluation Period for which urinalysis parameters were scheduled to be assessed, Last Value, EDV, and FV. Percentages for each parameter will be relative to the number of subjects with a result at each time point.

For occult blood, leukocytes, glucose, protein, ketones, and nitrates, the number and percentage of subjects with an on-treatment PCST value, PCST low value, and PCST high value will be summarized. This summary will consider all assessments after the first dose of BRV and prior to or on the date of the last dose of BRV. Percentages will be relative to the number of subjects with an on-treatment assessment.

Additionally, for occult blood, leukocytes, glucose, protein, ketones, and nitrates, the number and percentage of subjects with a PCST value, PCST low value, and PCST high value will be summarized for Baseline, Study Entry, each visit during the Evaluation Period for which laboratory parameters were scheduled to be assessed, EDV, Last Value, and FV. Percentages for each parameter and time point will be relative to the number of subjects with a value at that time point.

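### The nitrite PCST percentages in SAP 11.3.2 are 0% on the natural reading, because the 2-degree shift rule in 13.3.3 cannot be met on a two-level scale

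*SAP*

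**What the plan says.** SAP 11.3.2 (Macroscopic urinalysis) sets two kinds of scale. Five parameters are graded: "Response categories are negative, 1+, 2+, and 3+ for the qualitative urinalysis parameters occult blood, leukocytes, glucose, protein, and ketones". The sixth is binary: "and negative and positive for nitrates". Protocol 11.1.15 calls this test nitrites.

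The section then says how results are coded when PCST is determined: "Outcome values for these parameters are mapped to the levels Negative, 1+, 2+, and 3+ as follows for purposes of summary tables and the determination". The table that follows has four rows, and none mentions a result reported as positive.

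Three summaries in 11.3.2 name nitrates:

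- **Response categories.** "the number and percentage of subjects with each response category will be summarized for Baseline, Study Entry" and the later time points.
- **On-treatment PCST.** Occult blood is listed first, followed by: "leukocytes, glucose, protein, ketones, and nitrates, the number and percentage of subjects with an on-treatment PCST value, PCST low value, and PCST high value".
- **By-visit PCST.** The same three PCST results at Baseline, Study Entry, scheduled visits, EDV, Last Value and FV.

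The criterion is in SAP 13.3.3 (Urinalysis). On the scale it says: "For data analysis purpose, a four-point scale is used". A value is flagged "if an upward shift of at least 2 degrees from the baseline occurs under investigational treatment". The section explains how to shorten scales of five points or more. It does not mention a scale shorter than four.

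**The concern.** The criterion was written for graded results and is applied by name to a binary one. If a negative-to-positive change cannot meet it, the nitrite PCST row carries no information about the subjects. In the study report a structural 0% looks the same as an observed 0%, and a subject who turns nitrite-positive on treatment is counted in that row as having no PCST value.

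The row belongs to a committed analysis. Safety is the primary objective, laboratory tests including urinalysis are among the other safety variables (SAP 2.2.1.2), and protocol 13.1.3.1 promises a summary of possibly clinically significant treatment-emergent laboratory abnormalities.

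**Working it through.** The documents give no expected rate or other figure for this point, so there is nothing to reproduce. The check enumerates every pair of Baseline level b and on-treatment level t, computes shift = t − b, and counts the pairs with shift ≥ 2.

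**Inputs.** Levels: SAP 11.3.2. Threshold of 2, and upward direction only: SAP 13.3.3.

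**Step 1: graded parameters.** Code Negative = 0, 1+ = 1, 2+ = 2, 3+ = 3. There are 4 × 4 = 16 pairs. Those that qualify are:

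- Negative to 2+: 2 − 0 = 2
- Negative to 3+: 3 − 0 = 3
- 1+ to 3+: 3 − 1 = 2

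That is 3 of 16, with a maximum shift of 3. The rule works for these five parameters.

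**Step 2: nitrite on its own two levels.** Code negative = 0, positive = 1. There are 2 × 2 = 4 pairs, with shifts 0, 1, −1 and 0. The maximum is 1, below the threshold of 2, so 0 of 4 qualify.

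**Step 3: does the map in 11.3.2 rescue it?** Place positive at each level the map offers:

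| Positive placed at | Largest shift | Pairs with shift ≥ 2 | Support in the SAP map |
|---|---|---|---|
| 1+ | 1 | 0 of 4 | Nearest match: a single plus sign is in this row |
| 2+ | 2 | 1 of 4 | None: only 2+ or a double plus sign |
| 3+ | 3 | 1 of 4 | None: only results of 3+ or more |

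A non-zero rate needs positive to be placed at 2+ or 3+, and the SAP authorises neither.

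**Step 4: what the response-category table recovers.** It gives separate counts at each time point. One positive at Baseline and one at a later visit could be the same subject, with no change, or two subjects, one of them newly positive. The table cannot tell these apart, so it does not replace a paired result.

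**Step 5: the other cells.** A PCST low value would need a downward criterion, and 13.3.3 has none, so that row is empty for all six qualitative parameters. At Baseline the shift is b − b = 0, so the Baseline PCST column is empty too. By comparison, the pulse, blood pressure and adult weight criteria in SAP 13.3.4 also require a change from baseline, and the by-visit PCST list in SAP 11.4.1 starts at Study Entry and omits Baseline.

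**Step 6: a criterion that two levels can meet.** With a threshold of 1 for nitrite, 1 of the 4 pairs (negative to positive) qualifies and the row can be non-zero.

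**The case against.** The strongest reply is that little is lost. Nitrite positives appear by visit in the response-category table, source data are listed (SAP 3.1), and an abnormal laboratory finding can be an adverse event (protocol 12.1.1) and would then be counted among the TEAEs. This stands. A reader might infer that all nitrite output is forced to zero, or that positive results disappear from the report. The documents do not support that: what is lost is a paired, subject-level flag.

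A second reply is that, because positive has no row in the map, the criterion is undefined rather than provably zero. This stands in part. A programmer could place positive at 2+ or 3+ and obtain a non-zero rate, but that would be an undocumented choice. On the two-level reading, or with positive read as a plus sign, the result is zero. Either way the SAP needs correcting.

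A third reply is that a one-degree rise is not flagged for the graded parameters, so perhaps it should not be for nitrite. SAP 11.3.1 says the criteria rest on agency guidelines with sponsor additions, which are not reproduced. The documents therefore do not show that a one-step nitrite change must be flagged, and taking nitrite out of the PCST tables is an equally valid repair.

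Finally, it is tempting to multiply the 108 enrolled subjects (SAP 2.4) by an assumed conversion rate and report a number of missed cases. The documents give no such rate. The on-treatment denominator is subjects with an on-treatment assessment, and only those negative at Baseline could convert. No count is supportable.

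**Conclusion.** The point holds for the nitrite PCST summaries. SAP 11.3.2 and 13.3.3 together specify a result that, on the natural reading, is 0% on treatment and at every time point whatever the data: a maximum shift of 1 against a threshold of 2. This assumes that nitrite is reported on the two levels the SAP states and that positive is not assigned to 2+ or higher. The rule is sound for the five graded parameters.

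The consequence is small. It touches one supportive, descriptive laboratory table, with no hypothesis test and no primary safety variable involved. The empty PCST low rows and Baseline PCST column are a matter of table layout; no defined event is missed there, and they add no weight to the point.

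**What to change.** Choose one of two edits to the SAP:

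1. In 13.3.3, add a criterion that a two-level parameter can meet. For example, count nitrite as PCST high when it is negative at Baseline and positive on treatment, and describe this as an analysis flag.
2. In 11.3.2, remove nitrite from the PCST summaries and present a Baseline-to-on-treatment shift table instead.

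In either case, delete the PCST low rows and the Baseline PCST column for the qualitative urine parameters, and align the SAP's nitrates with the protocol's nitrites.

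The cost is one criterion or one replacement table, plus table-shell edits. No new data, visits or samples are needed. Under the first option a non-zero nitrite rate may appear, and it should be read as a laboratory flag only.

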### 13.3.4 Vital signs and body weight

|            |   |
|------------|---|
| Pulse rate | 
For 1 m to < 12 m: <math>\leq 110</math> bpm and a decrease of <math>\geq 20</math> bpm from baseline or <math>\geq 180</math> bpm and an increase of <math>\geq 20</math> bpm from baseline
 
For 12 m to < 3 y: <math>\leq 90</math> bpm and a decrease of <math>\geq 20</math> bpm from baseline or <math>\geq 150</math> bpm and an increase of <math>\geq 20</math> bpm from baseline
 
For 3 y to < 12 y: <math>\leq 65</math> bpm and a decrease of <math>\geq 20</math> bpm from baseline or <math>\geq 130</math> bpm and an increase of <math>\geq 20</math> bpm from baseline
 
For 12 y to < 17 y: <math>\leq 60</math> bpm and a decrease of <math>\geq 20</math> bpm from baseline or <math>\geq 120</math> bpm and an increase of <math>\geq 20</math> bpm from baseline
 
For <math>\geq 17</math> y: <math>\leq 50</math> bpm and a decrease of <math>\geq 30</math> bpm from baseline or <math>\geq 120</math> bpm and an increase of <math>\geq 30</math> bpm from baseline
 |
|------------|---|

bpm=Beats per minute.

|                          |   |
|--------------------------|---|
| Systolic blood pressure  | 
For 1 m to < 12 m: < 60 mmHg and a decrease of > 20 mmHg from baseline or > 110 mmHg and an increase of > 30 mmHg from baseline
 
For 12 m to < 6 y: < 70 mmHg and a decrease of > 20 mmHg from baseline or > 120 mmHg and an increase of > 30 mmHg from baseline
 
For 6 y to < 13 y: < 70 mmHg and a decrease of > 20 mmHg from baseline or > 130 mmHg and an increase of > 30 mmHg from baseline
 
For 13 y and < 17 y: < 90 mmHg and a decrease of > 20 mmHg from baseline or > 140 mmHg and an increase of > 30 mmHg from baseline
 
For ≥ 17 y: < 90 mmHg and a decrease of > 30 mmHg from baseline or > 180 mmHg and an increase of > 40 mmHg from baseline
 |
| Diastolic blood pressure | 
For 1 m to < 12 m: < 40 mmHg and a decrease of > 15 mmHg from baseline or > 60 mmHg and an increase of > 20 mmHg from baseline
 
For 12 m to < 6 y: < 45 mmHg and a decrease of > 15 mmHg from baseline or > 80 mmHg and an increase of > 20 mmHg from baseline
 
For 6 y to < 13 y: < 50 mmHg and a decrease of > 15 mmHg from baseline or > 85 mmHg and an increase of > 20 mmHg from baseline
 
For 13 y to < 17 y: < 55 mmHg and a decrease of > 20 mmHg from baseline or > 90 mmHg and an increase of > 30 mmHg from baseline
 
For ≥ 17 y: < 50 mmHg and a decrease of > 20 mmHg from baseline or > 105 mmHg and an increase of > 30 mmHg from baseline
      |
| Weight                   | 
For < 17 y: < 3% or > 97% of the normal body weight growth curve ranges for the age at date of weight assessment(a) and gender;
 
For ≥ 17 y: change of ≥ 7% of baseline weight
   |

(a) Once the subject reaches 17 years of age use the body curve criteria of a 17 year old regardless of their age in the study.

## 14 AMENDMENT(S) TO THE STATISTICAL ANALYSIS PLAN

### Rational for the amendment

The primary purpose for the amendment is (1) remove rules and definitions based on data cutoffs for interim analyses; (2) remove the summary analysis for direct cost parameter and indirect cost parameters, and as well as Socio-professional data.

### Change #1 (global)

Removed all rules and definitions based on data cutoffs for interim analyses throughout SAP.

### Change #2

#### Section 8.2.6 Direct cost parameters, Section 8.2.7 Indirect cost parameters, Section 8.2.8 Socio-professional data

Removed all direct/indirect cost parameters and socio-professional data summary analysis.

### Change #3

Removed signature page. Using e-signature approval process through Mikado.
